Using a split-mouth design, this study will evaluate soft tissue closure of extraction sockets by comparing sites treated with A-PRF to sites without A-PRF application at King Abdulaziz University Dental Hospital.

Significance of the Study

1. This research is expected to demonstrate the potential of A-PRF to enhance postoperative healing and improve the quality of life in diabetic patients undergoing dental extractions.
2. The findings may contribute to the development of improved, biologically based treatment protocols for diabetic patients in dental practice.

Literature Review

Diabetes Mellitus (DM) is a complex chronic disease affecting millions worldwide, with a notably elevated prevalence in Saudi Arabia. The increasing incidence of DM has been attributed to lifestyle changes, urbanization, and genetic predisposition. Microvascular complications such as retinopathy, nephropathy, and neuropathy significantly increase morbidity and mortality among diabetic patients.

In oral health, diabetes is associated with delayed wound healing, increased susceptibility to infection, periodontal disease, and tooth loss. The healing of extraction sockets normally progresses through distinct stages, including clot formation, inflammation, proliferation, and remodeling. However, in diabetic individuals, chronic hyperglycemia disrupts these processes by impairing angiogenesis, inflammatory regulation, collagen synthesis, and bone formation.

Platelet-rich fibrin (PRF) has emerged as a regenerative biomaterial capable of enhancing wound healing through sustained growth factor release. Advanced PRF (A-PRF), produced using low-speed centrifugation protocols, retains higher concentrations of platelets and leukocytes within a fibrin matrix. This biological scaffold is expected to improve cellular migration, angiogenesis, and tissue regeneration, making it particularly relevant for diabetic patients with compromised healing capacity.

Despite promising biological mechanisms, there remains limited clinical evidence evaluating the specific role of A-PRF in post-extraction socket healing in diabetic patients, highlighting the need for well-designed randomized clinical trials.

Materials and Methods

Study Design and Ethics

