This double-blinded, randomized controlled clinical trial will be conducted at King Abdulaziz University Dental Hospital. Ethical approval has been obtained from the Institutional Review Board, and the study will be conducted in accordance with the Declaration of Helsinki (2013). Written informed consent will be obtained from all participants prior to enrollment.

Sample and Study Population

The sample size has been calculated using G*Power software with an alpha level of 0.05, 80% power, and a medium effect size of 0.5. Diabetic patients aged 18 years or older requiring bilateral extraction of the same tooth type will be recruited. Patients with systemic conditions other than diabetes, bleeding disorders, pregnancy, lactation, or tobacco use will be excluded.

A split-mouth design will be employed, with one extraction site randomly assigned to receive A-PRF and the contralateral site serving as a control. Randomization will be performed using a computer-generated sequence. Patients and outcome assessors will remain blinded throughout the study.

Clinical Procedure

All extractions will be performed using a standardized atraumatic technique by a single calibrated operator. After extraction, venous blood will be collected to prepare A-PRF using a low-speed centrifugation protocol. The A-PRF membrane will be placed into the assigned socket, while control sockets will receive no adjunctive material. All sites will be sutured using standardized suture material.

Outcome Measures

Healing will be assessed quantitatively using digital intraoral scanning at baseline, 1 week, and 3 weeks post-extraction. Patient-reported outcomes, including pain, swelling, and satisfaction, will be collected using validated questionnaires at specified follow-up intervals.

Statistical Analysis

Data will be analyzed using Stata software (Version 16). Normality will be assessed using the Shapiro–Wilk test. Paired statistical tests will be used to compare healing outcomes between A-PRF-treated and control sites, with significance set at $p < 0.05$.

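### No pre-extraction pain or swelling score is scheduled, so side differences already present before extraction can be neither described nor used to gain precision

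*Combined protocol and SAP*

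**What the plan says.** Under Outcome Measures, two neighbouring sentences treat timing differently. For the scan: "Healing will be assessed quantitatively using digital intraoral scanning at baseline, 1 week, and 3 weeks post-extraction". For the symptoms: "Patient-reported outcomes, including pain, swelling, and satisfaction, will be collected using validated questionnaires at specified follow-up intervals". Those intervals are listed nowhere, and no pre-extraction symptom score is mentioned anywhere in the document. It is also not stated that pain and swelling are scored separately for each side.

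Under Sample and Study Population the design is split-mouth, with "one extraction site randomly assigned to receive A-PRF and the contralateral site serving as a control". On how the side is chosen: "Randomization will be performed using a computer-generated sequence". The two teeth must be of the same type, but no criterion asks for similar symptoms or a similar reason for extraction on both sides.

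Under Statistical Analysis: "Paired statistical tests will be used to compare healing outcomes between A-PRF-treated and control sites". No covariate is planned for any outcome, and no test is named specifically for pain or swelling. The Objectives section names only soft tissue closure. The title, research question and hypotheses also claim fewer post-extraction complications, and pain and swelling are the listed outcomes closest to that claim.

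**The concern.** Pairing removes what differs between patients. Pain or swelling on one side before extraction differs within the patient, so it stays in the A-PRF minus control difference. Randomising the side balances it on average, but in a trial of a few dozen pairs some chance imbalance will remain. A score taken before extraction would show that imbalance and let the analysis remove the part that persists to follow-up. Without one, the side comparison for pain and swelling may be noisier than it need be, and no reader could judge how alike the two sides were at the start. The information cannot be recovered once the teeth are out.

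**Working it through.** **Inputs from the plan.** Alpha 0.05, power 80% and effect size 0.5 (Sample and Study Population). No number of patients, sidedness or type of effect size is stated, so there is no planned figure to reproduce.

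**Assumptions, not in the documents.** Correlation r between the baseline side difference and the follow-up side difference: 0, 0.3, 0.5 and 0.7. For the points illustration in step 4: a 0–10 scale, an SD of the pre-extraction side difference of 2 to 4 points, and 0.2 to 0.5 of that difference persisting at follow-up.

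**Step 1: implied size.** A two-sided paired t-test with standardised difference 0.5 needs 34 pairs (power 80.8%). One-sided, it needs 27. I use 34.

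**Step 2: is the unadjusted comparison valid?** I simulated 34 pairs with 40,000 replicates, a built-in left–right baseline difference of 0.5 SD and the side randomised. With no treatment effect, the mean estimate is 0.000 to 0.001 SD and type I error is 5.0% to 5.2% at every r. With a true effect of 0.5, the mean estimate is 0.50. The chance imbalance carried into the mean difference has SD r/√34, which is 0.05, 0.09 and 0.12 SD units at r = 0.3, 0.5 and 0.7. The ordinary paired standard error already contains it.

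**Step 3: what adjustment gains.** The approximate proportional reduction in variance is 1 − (1 − r²) × 33/32. Pairs needed for 80% power, by the normal approximation, are ((1.960 + 0.842)/0.5)² × (1 − r²) = 31.4 × (1 − r²), rounded up. Power is simulated at 34 pairs with a true effect of 0.5; unadjusted it is about 81%.

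| r | Variance reduction | Power, adjusted | Pairs for 80% power |
|---|---|---|---|
| 0 | −3.1% (a loss) | 80% | 32 |
| 0.3 | 6.2% | 83% | 29 |
| 0.5 | 22.7% | 89% | 24 |
| 0.7 | 47.4% | 97% | 17 |

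The adjusted analysis keeps type I error at about 5% throughout.

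**Step 4: the same in points.** The 95% range of chance imbalance in the mean pre-extraction score is ±1.96 × SD/√34: ±0.67 for SD 2 and ±1.34 for SD 4. Multiplied by the persistence, 0.2 × 0.67 = 0.13 and 0.5 × 1.34 = 0.67 points. The upper figure combines the largest SD, the largest persistence and the 95% extreme. It also sits inside the ordinary interval: with slope 0.5 and r = 0.5 the follow-up difference has SD 0.5 × 4/0.5 = 4, so the 95% half-width is about 2.03 × 4/√34 = 1.4 points.

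**Step 5: how the covariate must enter.** If the baseline difference is centred at its sample mean, the regression intercept equals the unadjusted mean difference. Nothing is adjusted, yet the standard error shrinks. Simulated type I error is then about 6%, 9% and 16% at r = 0.3, 0.5 and 0.7. Entered uncentred, so that zero means equal sides, it stays at about 5%.

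**The case against.** A reader might infer that pre-existing one-sided pain biases the trial, or that an apparent A-PRF effect could merely reflect which side was worse beforehand. The documents do not support that. The side is randomised within each patient, so such pain favours neither treatment systematically, and step 2 shows error rates at their nominal level. What remains is the ordinary chance error that alpha controls.

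Four further objections have force.

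- **Persistence may be weak.** Extraction removes the tooth that may be causing the pain, so the correlation could be near zero. Adjustment then gains nothing and costs slightly.
- **The reading rests partly on silence.** The intervals are not listed, so follow-up only is the plain reading, not an explicit exclusion.
- **Baseline is undefined.** The plan does not say whether the baseline scan precedes extraction or when the side is assigned, so a suitable pre-extraction moment cannot be assumed to exist already.
- **Per-side scoring comes first.** If scores cover the whole mouth, there is no side contrast to adjust.

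The objective also names closure rather than symptoms, which limits the weight of the point. None of this removes the basic gap: a score that is not taken cannot be used or reported.

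**Conclusion.** The point holds as a cheap improvement in precision and reporting. It is not a validity flaw: an unadjusted paired comparison of randomised sides is sound. At 34 implied pairs the effect of adjustment runs from about a 3% loss of precision to a variance reduction of about 47%, and power from about 80% to 97% against 81% unadjusted. That range rests wholly on assumed correlations of 0 to 0.7, and on a two-sided paired test as the basis for 34 pairs. In a smaller trial the chance imbalance would be larger. The case for acting now is that the score is irrecoverable after extraction, and the cover letter states that nobody has yet been enrolled.

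**What to change.** In Outcome Measures, list the patient-reported time points and state that pain and swelling are scored separately for each side. Add one per-side score before extraction and before the side is revealed, and say where in the schedule this falls. Keep satisfaction at follow-up only.

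In Statistical Analysis, for pain and for swelling at each follow-up, regress the A-PRF minus control difference on the uncentred baseline A-PRF minus control difference, and report the intercept, with its confidence interval, as the treatment effect. State that the covariate is not mean-centred. Since the plan already checks normality, say also what will be done if scores cluster near zero at a late visit. Report the baseline scores by side.

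The cost is a few minutes of questionnaire before extraction and one degree of freedom, with little or no gain if pre-extraction symptoms do not predict postoperative ones.

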Cover Letter – Protocol Registration and Results System (PRS)

Date: Dec.13.2025

To:

Protocol Registration and Results System (PRS) Review Team

Subject: Protocol Registration Submission

Dear PRS Review Team,

We respectfully submit the study protocol entitled **“Application of Growth Factors Derived from Platelets to Accelerate Healing and Reduce Post-extraction Complications in Diabetic Individuals”** for registration in the Protocol Registration and Results System (PRS).

This protocol describes a **randomized, double-blinded, split-mouth clinical trial** that will be conducted at King Abdulaziz University Dental Hospital. The study is designed to evaluate the effect of **Advanced Platelet-Rich Fibrin (A-PRF)** on post-extraction soft tissue healing in patients with diabetes mellitus, a population known to exhibit impaired wound healing and increased susceptibility to postoperative complications.

The study will enroll adult diabetic patients requiring bilateral extraction of the same tooth type. One extraction socket will be randomly assigned to receive A-PRF, while the contralateral socket will serve as a control. Healing will be assessed using **digital intraoral scanning at predefined time points**, along with patient-reported outcome measures. The split-mouth design has been selected to minimize inter-individual variability and improve internal validity.

The protocol has been developed in accordance with ethical and methodological standards for human clinical research. Ethical approval has been obtained from the Institutional Review Board of King Abdulaziz University Dental Hospital, and the study will be conducted in compliance with the Declaration of Helsinki. Written informed consent will be obtained from all participants before enrollment. At the time of registration, no participants have been enrolled, and no data have been collected.

This registration is being submitted to ensure **transparency, methodological rigor, and prospective documentation** of the study design and planned analyses. We confirm that the information provided in the PRS submission accurately reflects the study protocol and that study results will be reported in accordance with PRS requirements upon completion.

Thank you for your review and consideration of this protocol registration. Please do not hesitate to contact us if you require any additional information or clarification.

Sincerely,

[name] [name]

Principal Investigator

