King Abdulaziz University Dental Hospital

Jeddah, Saudi Arabia

Email: [your institutional email]

On behalf of the study team:

[name]; [name]; [name]

**Application of Growth Factors Derived from Platelets to Accelerate Healing and Reduce
Post-Extraction Complications in Diabetic Individuals**

Authors

[name]*, [name]*, [name]

Abstract

Introduction

Diabetes Mellitus (DM) represents a significant global public health challenge, with a particularly high prevalence in Saudi Arabia. The increasing incidence of DM has raised concerns regarding optimal management strategies for surgical procedures such as dental extractions. Diabetic individuals frequently experience impaired postoperative healing due to compromised tissue repair mechanisms and increased susceptibility to infection. Conventional management approaches may be insufficient, highlighting the need for biologically driven adjunctive therapies.

Objective

This study aims to evaluate the clinical effectiveness of Advanced Platelet-Rich Fibrin (A-PRF) in enhancing soft-tissue healing and reducing post-extraction complications in diabetic patients.

Methods

A randomized, double-blinded, split-mouth clinical trial will be conducted at King Abdulaziz University Dental Hospital. Diabetic patients requiring bilateral extraction of the same tooth type will be enrolled. One extraction socket will be randomly assigned to receive A-PRF, while the contralateral socket will serve as the control. Healing will be assessed using digital intraoral scanning at baseline, 1 week, and 3 weeks post-extraction. Statistical analysis will be performed using paired-comparative tests, with a significance level of $p < 0.05$.

Expected Outcomes

The application of A-PRF is expected to enhance soft tissue healing and reduce postoperative complications in diabetic individuals.

Conclusion

This study is expected to provide clinical evidence supporting the use of A-PRF as a biologically based adjunctive approach to improve post-extraction healing outcomes in diabetic patients.

Introduction

Diabetes Mellitus (DM) is a global public health problem, with an especially high prevalence in Saudi Arabia. The rising incidence of DM has increased concerns regarding the management of diabetic patients undergoing surgical procedures, including tooth extractions. Diabetic individuals often exhibit impaired postoperative healing characterized by delayed tissue repair,

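### Soft tissue closure is the objective, but no scan metric, primary visit or testing order is named, so the stated 5% alpha and 80% power belong to no single comparison

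*Combined protocol and SAP*

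**What the plan says.** - **Objective.** The Objectives section states that "this study will evaluate soft tissue closure of extraction sockets by comparing sites treated with A-PRF to sites without A-PRF application". It gives no metric and no visit.
- **Assessments.** Under Outcome Measures, "Healing will be assessed quantitatively using digital intraoral scanning at baseline, 1 week, and 3 weeks post-extraction". The Methods paragraph of the Abstract repeats the schedule without ranking the visits. The cover letter refers only to "digital intraoral scanning at predefined time points". Pain, swelling and satisfaction are also collected, and are not labelled secondary.
- **Sample size.** The calculation is described as made "with an alpha level of 0.05, 80% power, and a medium effect size of 0.5". The resulting number of patients, the sidedness, the outcome and the visit are not given.
- **Analysis.** "Paired statistical tests will be used to compare healing outcomes between A-PRF-treated and control sites", at p < 0.05. The outcomes are plural and the tests are not named. "Normality will be assessed using the Shapiro–Wilk test", but the plan does not say which paired test follows from the result.
- **Hypotheses.** The alternative hypothesis has a direction (A-PRF is better) and two parts (faster healing, and fewer complications).
- **Timing.** The cover letter says that recruitment had not begun at registration.

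No section names a primary outcome, a primary visit, a testing order or a multiplicity adjustment.

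**The concern.** There are two post-treatment healing comparisons and one error budget. An analyst who follows the plan to the letter could test week 1 and week 3 at 0.05 each and rest the trial's claim on whichever is significant. Nothing in the plan forbids this, and nothing requires it.

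The two possible decision rules damage different properties. If either visit is enough, the false-positive risk exceeds the level of a single test. If both visits must succeed and the sample was sized for one test, power falls below the stated 80%. A reader of the results could not tell which rule had applied, so could not check the stated 5% and 80% against them. The undefined scan metric adds to the problem, since an area, a distance, a volume or a change from baseline could each be put forward as closure.

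**Working it through.** **Inputs from the plan:** alpha 0.05, power 80%, effect size 0.5, two follow-up scans, paired tests.

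**Assumptions (not in the plan):** the correlation rho between the two visits' test statistics, the sidedness, and the number of pairs. The 0.5 is read as the standardised within-patient difference. The plan prints no sample size and no overall error rate, so there is no figure to reproduce.

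**1. Reference number of pairs.** Paired t-test, noncentral t with noncentrality 0.5 × √n:
- Two-sided 0.05: power is 0.795 at n = 33 and 0.808 at n = 34, so 34 pairs.
- One-sided 0.05: power is 0.812 at n = 27, so 27 pairs. A two-sided 0.05 test with 27 pairs has power 0.706.

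**2. Either visit enough, no true effect.** For one measure at two visits, with jointly normal statistics:

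error = P(test 1 significant) + P(test 2 significant) − P(both significant)

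With two-sided 0.05 tests and rho = 0, this is 0.05 + 0.05 − 0.0025 = 0.0975. The other entries use the bivariate normal distribution.

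| rho | Two-sided 0.05, any significant result | Two-sided 0.05, only results favouring A-PRF | One-sided 0.05 |
|---|---|---|---|
| 0 | 9.75% | 4.9% | 9.75% |
| 0.5 | 9.1% | 4.5% | 8.8% |
| 0.7 | 8.3% | 4.2% | 8.0% |
| 0.9 | 7.0% | 3.5% | 6.8% |
| 0.99 | 5.7% | 2.8% | 5.6% |
| *Level of one test* | *5%* | *2.5%* | *5%* |

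Simulated two-sided paired t-tests with 34 pairs agree: about 9.7%, 9.1% and 7.8% at rho 0, 0.5 and 0.8.

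**3. Limits of the 9.75% ceiling.** It needs one measure, exactly two visits and jointly normal statistics. Without normality the bound is 0.05 + 0.05 = 10%. With more measures it no longer applies: three independent tests give 1 − 0.95³ = 14.3%, and five give 1 − 0.95⁵ = 22.6%.

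**4. Both visits required.** With 34 pairs, effect 0.5 at both visits and two-sided 0.05 tests (200,000 simulated trials per value), joint power is 65%, 70%, 72%, 76% and 77% at rho 0, 0.5, 0.7, 0.9 and 0.95. Check at rho 0: 0.808² = 0.653.

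**5. Alpha split, 0.025 per visit (two-sided).** Power at each visit is 0.713 with 34 pairs and 0.805 with 41 pairs.

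**The case against.** **The target can be identified.** The Objectives section gives one objective, soft tissue closure, and the Abstract puts soft-tissue healing first. This stands in part. A reader might infer that the trial has no intended healing outcome at all, and the documents do not support that. What is missing is the metric, the visit and the formal primary status.

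**The inflation is conditional.** No section states an either-visit rule, or even that each visit is tested separately. If the visits are highly correlated, the excess is modest (7.0% at rho 0.9). This stands. A reader might infer that the trial runs at a 9.75% error rate, but that is one scenario at one assumed correlation. What is established is that the plan permits it.

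**The hypothesis has a direction.** If two-sided 0.05 tests are used and only a result favouring A-PRF supports the claim, the either-visit error stays below 5%. This stands as arithmetic, so it would be wrong to say that the error exceeds 5% under every reading. It still exceeds the 2.5% that one such test allows in that direction, and with one-sided 0.05 tests it exceeds 5%.

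**The visits might be given equal standing by design.** The Abstract and Outcome Measures list both without ranking them, but the cover letter names no visit. The documents show the absence of a ranking, not a decision to treat the visits as co-primary.

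**Test form is a separate matter.** There is more than one defensible paired test. The point here is only that it should be chosen in advance.

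**Conclusion.** The point holds as a gap in specification with a bounded consequence. The plan's single alpha, power and effect size are attached to no defined measure and no visit, and no rule says how two follow-up results combine into one claim.

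- **If either visit suffices** (one measure, jointly normal statistics, rho 0 to 0.99): the error is 9.75% to 5.7% two-sided against 5%; 4.9% to 2.8% against 2.5% if only results favouring A-PRF count under two-sided tests; or 9.75% to 5.6% against 5% with one-sided tests. Several scan measures would raise it further.
- **If both visits are required** (34 pairs inferred, effect 0.5 at both, rho 0 to 0.95): power is about 65% to 77% against the stated 80%.

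That no metric, visit or order is named is certain from the text. The sizes rest on assumed correlation, sidedness and number of pairs. The matter concerns the trial's main claim and cannot be settled credibly once data are seen, so it should be fixed before enrolment.

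**What to change.** **Change.** Before the first patient is enrolled:
1. Define one scan-derived measure of soft tissue closure at one visit, week 1 or week 3 as the sponsor chooses, as the single primary within-patient comparison.
2. State its sidedness and name its paired test in advance.
3. Tie the alpha of 0.05, the 80% power and the effect size of 0.5 to that comparison, and print the number of pairs.
4. Test the same measure at the other visit in fixed sequence, only if the primary is significant. This holds the error over the two tests to the level of one.
5. Report pain, swelling, satisfaction and complications as secondary, with 95% confidence intervals, and say plainly that the complications half of the alternative hypothesis is then not confirmatory.

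**Cost.** Wording only, if the planned number gives at least 34 complete pairs and the test is two-sided. If it came from a one-sided calculation (27 pairs) and the test is two-sided, power must be restated as about 71%; reaching 34 takes 34 − 27 = 7 more pairs. A result significant only at the other visit is no longer confirmatory, and success at both visits has the joint power shown above.

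**Alternative.** If the sponsor wants either visit to be able to succeed, test the same measure at both visits at 0.025 each (Bonferroni) and state that power at each visit is 71% with 34 pairs. Restoring 80% at each visit takes 41 pairs, 7 more than 34.

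### The baseline intraoral scan has no stated role in the analysis; if it is taken after extraction and before A-PRF placement, adjusting for it is a cheap improvement in precision

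*Combined protocol and SAP*

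**What the plan says.** Under Outcome Measures the plan states: "Healing will be assessed quantitatively using digital intraoral scanning at baseline, 1 week, and 3 weeks post-extraction". The objective is framed as closure: "this study will evaluate soft tissue closure of extraction sockets by comparing sites treated with A-PRF to sites without A-PRF application".

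The Statistical Analysis section names the software, a Shapiro–Wilk check and a significance level of 0.05. On the comparison itself it says only "Paired statistical tests will be used to compare healing outcomes between A-PRF-treated and control sites". The abstract adds nothing further: "Statistical analysis will be performed using paired-comparative tests".

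The documents do not say whether the analysed value is the follow-up measurement, the change from baseline or percent closure, and they mention no covariate. They also do not say when the baseline scan is taken relative to extraction, A-PRF placement and suturing. The Cover Letter gives the reason for pairing: "The split-mouth design has been selected to minimize inter-individual variability and improve internal validity".

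**The concern.** Pairing removes what one patient's two sockets have in common. It does not remove what differs between them, such as a larger opening on one side at the start. If that difference carries through to the follow-up scan, it adds noise to the within-patient comparison. A scan of both sockets after extraction and before placement would measure it, and a baseline scan is already scheduled.

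The present wording lets the baseline be ignored, subtracted or used as a denominator. These choices can differ materially in power, and nothing in the plan decides between them. What is at stake is precision and a clearly pre-specified analysis, not bias.

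**Working it through.** **Inputs from the documents.** The sample-size statement gives "an alpha level of 0.05, 80% power, and a medium effect size of 0.5". It gives no number of patients, no sidedness, no standard deviation and no correlation, so there is no stated figure to reproduce.

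**Implied number of pairs.** Taking 0.5 as the standardised paired difference (dz), the noncentral t distribution gives:
- two-sided: 34 pairs, power 80.8% (33 pairs give 79.5%);
- one-sided: 27 pairs, power 81.2%. A two-sided test with 27 pairs has 70.6%.

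The rest uses 34 pairs, two-sided 0.05, with 27 pairs as a check. These are assumptions.

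**Assumed quantity.** Let r be the correlation, across patients, between the baseline difference and the follow-up difference (A-PRF minus control in each case). It is not in the documents; the range 0 to 0.7 is shown.

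**Unadjusted paired test.** The noncentrality is 0.5 × √34 = 2.915 on 33 df.

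**Adjusted analysis.** The model is follow-up difference = a + b × baseline difference + error, and the intercept a is the treatment effect. Residual variance is multiplied by 1 − r². Estimating the slope costs one degree of freedom and inflates the variance of the intercept by 1 + 1/(n − 3) = 32/31 on average. The noncentrality is therefore about 2.915 / √[(1 − r²) × 32/31] on 32 df: 2.870, 3.008, 3.314 and 4.018 at r = 0, 0.3, 0.5 and 0.7. Simulation with 100,000 runs per cell gives:

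| r | 1 − r² | Unadjusted, 34 pairs | Adjusted, 34 pairs | Gain (points) | Unadjusted, 27 pairs | Adjusted, 27 pairs |
|---|---|---|---|---|---|---|
| 0 | 1.00 | 80.6% | 79.4% | −1.2 | 70.7% | 68.8% |
| 0.3 | 0.91 | 81.0% | 83.2% | +2.2 | 70.7% | 72.8% |
| 0.5 | 0.75 | 80.8% | 89.4% | +8.6 | 70.6% | 80.8% |
| 0.7 | 0.51 | 80.8% | 97.2% | +16.4 | 70.5% | 92.9% |

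Simulated type I error of the adjusted test at 34 pairs is 4.9 to 5.1%.

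**Subtracting the baseline instead.** Let k be the SD of the baseline differences divided by the SD of the follow-up differences. The change score has relative variance 1 + k² − 2rk, which at k = 1 is 2(1 − r). Power at 34 pairs is then 51.5, 66.6, 80.8 and 95.4% at the same four values of r. Subtraction thus loses to ignoring the baseline when r is below 0.5 and gains when it is above.

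**Percent closure.** The table assumes that healing is additive on the raw scale. Suppose instead that each socket heals by a fraction of its own starting size. Assume 34 pairs, an effect of 0.5 on the scale of the fraction difference, a between-patient coefficient of variation in socket size of 0.2 to 0.8, and 5 to 20% variation in size between a patient's two sockets. Then:
- a paired test of percent closure has about 81% power;
- the adjusted analysis of raw size has about 61 to 78%, lower as socket sizes vary more between patients;
- the gap is about 81 − 78 = 3 to 81 − 61 = 20 points;
- adding the baseline difference as a covariate to percent closure costs about 1 point.

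The case for adjustment is therefore separate from the choice of metric.

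**The case against.** **The planned test is not wrong.** This stands in full. A reader might infer that omitting the baseline biases the comparison. It does not: the side is randomised and the paired test is valid.

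**The gain may be small.** This stands too. Pairing, the same tooth type on both sides, one calibrated operator and a standardised technique may leave little real difference between a patient's sockets at the start. At r between 0 and 0.3 the change is only about −1 to +2 points, and nothing in the documents supports the larger values of r.

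**The baseline scan may not be usable.** The plan does not time it. If it precedes extraction, it does not measure the socket. If it follows placement, it may already be affected by treatment. The condition must therefore be part of the recommendation. An interval for a suitable scan does exist, since "After extraction, venous blood will be collected to prepare A-PRF using a low-speed centrifugation protocol".

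**Adjustment of raw size is not best under every model.** This is correct. A reader might infer that percent closure should be demoted to a secondary analysis. The proportional-healing results show that this could cost power, and closure is the stated objective.

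**Metric and visit come first.** Also correct: the plan names no primary scan metric or visit, and the adjustment can only be written once both are chosen. That governs the order of the edits and does not remove the gain.

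**Conclusion.** The point holds as an inexpensive improvement to a valid plan. With 34 pairs and dz = 0.5, both assumed, adjustment costs about 1 point of power if the baseline is uninformative (about 2 points at 27 pairs). It gains about 2, 8 to 9 and 16 points over the unadjusted paired test at r = 0.3, 0.5 and 0.7. Where the true r lies is unknown. The benefit also requires a scan of the socket after extraction and before A-PRF placement, which the documents do not establish.

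A reader might also infer that the plan runs an inflated false-positive rate. If the raw or the change-score test were picked after seeing the results, type I error would be about 6 to 10%. The documents do not say that such a choice will be made, and naming any single analysis in advance removes the problem. That figure is a reason to pre-specify one analysis; it is not evidence for adjustment.

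The point concerns the scan outcome only. No baseline is described for pain, swelling or satisfaction.

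**What to change.** 1. State when the baseline scan is taken relative to extraction and A-PRF placement.
2. Name one scan metric and one primary visit. Raw size and percent closure are both acceptable; the plan should not rank raw size above percent closure.
3. If the scan falls after extraction and before placement, make the primary analysis a regression of the within-patient difference in that metric (A-PRF minus control) on the within-patient baseline difference. Report the intercept with its 95% CI as the treatment effect. For percent closure, use a baseline difference such as the log ratio of the two socket sizes as the covariate.
4. If the scan falls at any other time, use the unadjusted paired difference at the primary visit. Percent closure would then share the problem, because its denominator is the same scan.
5. Check normality on the regression residuals. If it fails, test the intercept by a sign-flip randomisation test that flips each patient's baseline and follow-up differences together.

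The cost is one paragraph of text and a few lines of Stata, with no added patients. No added scan is needed if baseline already falls in the required interval; if not, its timing has to be set. The statistical price is the 1 to 2 points of power given above. The Cover Letter states that no participants had been enrolled at registration, so on that statement the analysis could be specified before any data exist.
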